2.5.3 Handling of intercurrent events

For AEs, SAEs, important identified and important potential risks, intercurrent events will not be considered following a treatment policy strategy.

Use of prohibited concomitant medications with an impact on safety: Data collected while/after receiving prohibited concomitant medications with an impact on safety will be included in the analyses of AEs (treatment policy strategy).

Study discontinuation due to reasons other than death: Data collected up to the point of discontinuation will be included in all primary endpoint analyses.

Study discontinuation due to death: It is anticipated that this intercurrent event is unlikely to occur during the study. Data collected up to the point of death will be included in all primary endpoint analyses.

Changes from baseline in vital signs, clinical laboratory, and procedure results will be summarized for all data available, only excluding data collected after the start of intake of prohibited medication, if any, following a hypothetical strategy and assuming this intercurrent event occurring at random.

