1.2.1 Primary estimand(s)

The clinical question of interest: What is the safety of single administration of IV OAV101 treatment in SMA participants that weigh ≥ 8.5 to ≤ 21 kg?

The primary estimand is described by the attributes listed below.

The population of interest is participants with SMA that weigh ≥ 8.5 to ≤ 21 kg

The primary variables include:

1. Treatment emergent AEs and SAEs
2. Important identified and important potential risks
3. Change from baseline in vital signs, cardiac safety assessments, and clinical laboratory results

The treatment of interest is IV OAV101.

The remaining intercurrent events include receiving prohibited concomitant medications with an impact on safety, such as concomitant medication with the intent to treat SMA. All observed AE/SAE/AESI will be reported (treatment policy strategy). For primary variable 3, if participants take prohibited concomitant medications, all the measures taken after will be disregarded as missing data and handled by a hypothetical strategy under the assumption of missing at random.

The summary measures include incidence and severity for treatment emergent AEs and SAEs as well as important identified and important potential risks and mean for changes from baseline in vital signs and clinical laboratory results.

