1.2.2 Secondary estimand(s)

The secondary clinical question of interest: What is the efficacy of single administration of IV OAV101 treatment in SMA participants that weigh ≥ 8.5 to ≤ 21 kg?

The secondary estimand is described by the attributes listed below.

The population of interest is patients with SMA that weigh ≥ 8.5 to ≤ 21 kg.

The secondary variables include:

1. Change from baseline in Hammersmith Functional Motor Scale - Expanded (HFMSSE), as appropriate according to participant age.
2. Change from baseline in Revised Upper Limb Module (RULM), as appropriate according to participant age.
3. Achievement of developmental motor milestones according to the World Health Organization-Multicentre Growth Reference Study (WHO-MGRS) and Bayley Scales of Infant and Toddler Development - Third Ed (Bayley-III) criteria.
 - holds head erect for at least 3 seconds without support
 - sits with slight support 30 seconds
 - sitting without support
 - sits without support 30 seconds

- hands-and-knees crawling
- pulls to stand
- standing with assistance
- walking with assistance
- standing alone
- walking alone

The treatment of interest is IV OAV101.

The remaining intercurrent events include receiving prohibited concomitant medications with an impact on efficacy, such as SMN-targeting and investigational SMA medications. Loss to follow-up due to reasons other than death will be handled by a hypothetical strategy for the change from baseline variables and by a composite strategy for milestones.

The summary measures include mean for changes from baseline in HFMSE and RULM as well as incidence for milestone achievement.

2 Statistical methods

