2.5.5 Sensitivity analyses

Given the descriptive nature of the summary of primary safety endpoints, no sensitivity analysis is planned. Only if intercurrent events of intake of prohibited concomitant medication with the intent to treat SMA will occur, in a sensitivity analysis of changes from baseline in vital signs, ECG and laboratory parameters all data including those collected after the intercurrent event started will be considered following a treatment policy strategy.

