2.6.3 Handling of intercurrent events

Changes in HFMSE and RULM and developmental motor milestone achievements will be summarized for all data available, only excluding data collected after the start of intake of prohibited medication with an impact on efficacy, if any, following a hypothetical strategy and assuming this intercurrent event occurring at random.

Following a composite strategy, in participants of the FAS dying before the achievement of a developmental motor milestone, the milestone is assumed not being achieved at any of the visits planned after the death occurred.

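### SAP 2.5.5 does not restore everything that 2.5.3 removes from primary endpoint 3 (echocardiogram is left out), and the excluding sentences lack their safety qualifier

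*SAP*

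**What the plan says.** **Scope of the endpoint.** SAP 2.5.1 defines primary endpoint 3 as change from baseline in vital signs, clinical laboratory and procedure results. It names ECG and echocardiogram as the procedures.

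**The event and the exclusion.** SAP 1.2.1 introduces the intercurrent event as "receiving prohibited concomitant medications with an impact on safety, such as concomitant medication with the intent to treat SMA". Later in the same paragraph, the rule for variable 3 reads "if participants take prohibited concomitant medications, all the measures taken after will be disregarded as missing data". SAP 2.5.3 keeps the qualifier where data are retained: "Data collected while/after receiving prohibited concomitant medications with an impact on safety will be included in the analyses of AEs". Its last paragraph covers changes in vital signs, laboratory and procedure results. It removes data without the qualifier, "only excluding data collected after the start of intake of prohibited medication, if any, following a hypothetical strategy", and assumes that the event occurs at random.

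**The sensitivity analysis.** SAP 2.5.5 opens with its trigger, "Only if intercurrent events of intake of prohibited concomitant medication with the intent to treat SMA will occur, in a sensitivity analysis", and continues with its scope, "of changes from baseline in vital signs, ECG and laboratory parameters all data including those collected after the intercurrent event started will be considered".

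**The efficacy counterpart.** SAP 1.2.2 describes the event as "receiving prohibited concomitant medications with an impact on efficacy, such as SMN-targeting and investigational SMA medications". The excluding sentence in 2.6.3 keeps that limit: "only excluding data collected after the start of intake of prohibited medication with an impact on efficacy, if any".

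**What is prohibited.** Protocol 6.2.2 lists SMA-intent medication, other investigational medication, non-live vaccines in the 4 weeks after infusion, live vaccines during corticosteroids, and immunosuppressive therapies. Non-live vaccines and immunosuppressants needed to treat an adverse event are exempt. Protocol 6.2.1 encourages routine immunization consistent with those limits.

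**The concern.** A sensitivity analysis for an exclusion should put back whatever the exclusion took out. Here it does not. Endpoint 3 is an available-case descriptive summary (SAP 2.5.2), so an excluded value simply drops out and no model makes use of the child's other data. The treatment is a single, irreversible dose, so values recorded after another medication are still part of the safety follow-up that the primary objective asks for. Cardiac adverse events are among the listed important risks, yet echocardiogram is the component with no route back.

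The second issue is the trigger. The qualifier stands where the event is introduced and where data are kept, but not in the two sentences that remove data, and the SAP never defines an impact on safety. Two programmers could build different endpoint-3 tables from the same data. Under the literal reading, the at-random assumption is also doubtful for live vaccines. Prednisolone continues until liver tests return to baseline (protocol 6.2), so that window stays open longest in children with persistent liver elevations.

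**Working it through.** **The plan's own figure.** No figure in the plan attaches to this rule. The only design figure is a 90% chance of seeing at least one event with about 24 participants at 9% incidence. It reproduces: 1 − 0.91^24 = 0.896. It concerns event incidence, for which AE data are all kept, and is not in dispute.

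**What 2.5.3 removes against what 2.5.5 restores.**

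| Component of endpoint 3 | After SMA-intent medication | After any other excluded medication |
|---|---|---|
| Vital signs | restored | not restored |
| Laboratory | restored | not restored |
| ECG | restored | not restored |
| Echocardiogram | not restored | not restored |

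The echocardiogram gap after SMA-intent medication holds whichever way the trigger is read. The right-hand column matters under the narrow reading too, because 1.2.1 gives SMA-intent medication only as an example of a medication with a safety impact.

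**Visits lost per child under the literal reading.** Inputs from SAP 2.1.1, as nominal days:
- All follow-up visits, with vital signs at each (SAP 2.5.1): 8, 15, 22, 29, 43, 57, 71, 92, 183, 274, 365 (11 visits).
- ECG and echocardiogram: 8, 29, 57, 92, 183, 365 (6 visits).

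The shortest steroid course follows from protocol Table 6-2: 1 mg/kg through Day 30, then 0.75 on Days 31–37, 0.5 on Days 38–44 and 0.25 on Days 45–51. Protocol 6.2 also foresees courses longer than 60 days. The vaccine days below are assumptions; the counts are the visits that fall after them.

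| Assumed vaccine day | Type | Follow-up visits lost (of 11) | ECG/echocardiogram visits lost (of 6) |
|---|---|---|---|
| 9 | non-live | 10 | 5 |
| 28 | non-live | 8 | 5 |
| 30 | live | 7 | 4 |
| 51 | live, end of shortest course | 6 | 4 |
| 60 | live, longer course | 5 | 3 |

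No laboratory visit count is given, because the laboratory rows of Table 8-1 were not readable in the copy used. If the exclusion is limited to medication with a safety impact and the vaccine is judged to have none, the loss is 0 visits.

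**Effect on a mean.** Let one child have value x, let m be the mean of the other n − 1 children, and let d = x − m. The mean with the child is ((n − 1)m + x)/n = m + d/n, so dropping the child moves the mean by d/n. Assume d = 2 × ULN for ALT:
- Bracket of 10: 2/10 = 0.20 × ULN. Bracket of 6: 2/6 = 0.33 × ULN.
- Overall, 30 children: 2/30 = 0.07 × ULN. Overall, 24 children: 2/24 = 0.08 × ULN.

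The shift scales with d. The median may not move at all.

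**The case against.** The strongest reply is that context already supplies the qualifier. In 1.2.1 the rule for variable 3 follows within the paragraph that defines the event as medication affecting safety. The closing words of 2.5.3 speak of this intercurrent event, which points back to the event just described with the qualifier. The SAP's primary estimand defines no other prohibited-medication event, and the SAP says that it supersedes the protocol's statistical considerations. This largely stands. A reader might infer that children vaccinated inside a window will lose their primary safety data. The documents do not support that: they support an ambiguity, and the narrower reading is the more natural one.

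A reader might also infer that safety signals would be hidden. That is not supported either. AEs, SAEs and AESIs follow treatment policy, and SAP 2.1 lists all individual data. The shift tables, ALT threshold counts and individual laboratory courses (2.5.2), and the liver criteria including Hy's Law (2.7.3), carry no stated exclusion. SAP 2.7.4 also promises descriptive echocardiogram summaries without stating one, although it refers to 2.5 for the changes. The absence of an end date is not a separate defect, since 2.6.3 has none.

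Finally, the trigger is a protocol deviation of unknown frequency, and the ALT difference above is assumed. Both points are correct and limit the size of the issue. None of this closes the mismatch between 2.5.3 and 2.5.5.

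**Conclusion.** The point holds as a minor one. The firm part is that 2.5.5 restores less than 2.5.3 removes: echocardiogram never, and nothing after a prohibited medication other than one intended to treat SMA. The softer part is that the excluding sentences lack the qualifier, so that read literally they reach in-window vaccines.

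Per affected child under that literal reading, 5 to 10 of 11 follow-up visits and 3 to 5 of 6 cardiac visits would drop out for the vaccine days considered. One child is 1/10 to 1/6 of a bracket. These figures rest on assumed vaccine days. The documents give no rate of prohibited medication use, so the number of children affected may be zero. Only untested, descriptive change-from-baseline summaries are exposed.

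A reader might go further and conclude that every listed medication other than SMA-directed or investigational drugs should follow treatment policy. The argument about vaccines does not carry over to immunosuppressants given for reasons other than an adverse event. These could reasonably count as affecting safety, and how to handle them is the sponsor's estimand choice.

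**What to change.** Two wording changes before database lock.

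1. **SAP 2.5.5**, replace the trigger and scope with: *If any value is excluded under Section 2.5.3, changes from baseline in vital signs, laboratory, ECG and echocardiogram parameters are also summarized with all excluded values restored (treatment policy).*
2. **SAP 1.2.1 and the last paragraph of 2.5.3**, add the safety-impact qualifier to the excluding sentences and state: *Vaccines listed in protocol Section 6.2.2 do not trigger exclusion.* Leave immunosuppressants not given for an adverse event to the sponsor's definition of a safety impact.

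The cost is one extra descriptive summary, run only if a value is excluded. No new assessments, participants or protocol amendment are needed, because concomitant medications are already recorded on the CRF. A line in SAP Section 4 would be prudent, since protocol 2.1 names prohibited medication as an intercurrent event without the qualifier.

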2.5.4 Handling of missing values not related to intercurrent event

Missing values not related to intercurrent events will not be imputed. All data of participants in the safety set will be presented as observed, collected and derived.

2.5.5 Sensitivity analyses

Given the descriptive nature of the summary of primary safety endpoints, no sensitivity analysis is planned. Only if intercurrent events of intake of prohibited concomitant medication with the intent to treat SMA will occur, in a sensitivity analysis of changes from baseline in vital signs, ECG and laboratory parameters all data including those collected after the intercurrent event started will be considered following a treatment policy strategy.

2.5.6 Supplementary analyses

No supplementary analysis is planned.

2.6 Analysis supporting secondary objectives

2.6.1 Secondary endpoint(s)

The secondary endpoints include:

1. Changes from baseline in HFMSE and RULM;
2. Percent of participants achieving development motor milestones according to the WHO-Multicenter Growth Reference Study (WHO-MGRS) and Bayley Scale of Infant and Toddler Development - Third Ed (Bayley-III) criteria.

For all participants of 24 months of age or more at the time of visit, HFMSE (2019 edition) will be assessed, consisting of 33 SMA-specific items with a maximal total score of 66 (O'Hagen et al 2007). Each item is scored on a 3-point Likert scale from 0 (no response) to 2 (full response) and summed up to the total score. A higher score indicates a higher ability level. A total score will not be derived if any item score is missing or "cannot test".

For all participants of 30 months of age or more at the time of visit, RULM will be assessed, consisting of 19 items with a maximal total score of 37 with lower scores reflecting poorer ability. RULM is an assessment that measures motor performance in the upper limbs from childhood to adulthood in ambulatory and non-ambulatory individuals with SMA. There are 18 items scored 0 (unable) to 2 (full achievement) and one item scored 0 (unable) to 1 (able) summed up to the total score (Pera et al 2019). For participants of 24 to 30 months of age at the time of visit, the two test items (C)- Tracing a path and (H)- Tearing Paper will not be administered and therefore for a participant between the ages of 24-30 months the maximum score achieved is 33 points. A total score will not be derived if any item score is missing or "cannot test".

Changes from baseline are only summarized for subjects whose baseline values are available. For younger subjects who are not eligible for RULM/HFMSE measure at baseline, their scores at later visits will only be listed.

The Developmental Milestone Checklist consists of 10 Developmental Motor Milestones obtained from WHO-MGRS (sitting without support, hands-and-knees crawling, standing with assistance, walking with assistance, standing alone, and walking alone) and from Bayley-III (head control (Bayley gross motor item #4), sits with slight support for at least 30 seconds (Bayley gross motor item #19), sits without support for at least 30 seconds (Bayley gross motor item #26), and pulls to stand (Bayley gross motor item #35)) (WHO Multicentre Growth Reference Study Group 2006, Bayley 2006).

2.6.2 Statistical hypothesis, model, and method of analysis

No hypothesis testing will be performed.

The secondary endpoints will be summarized by weight bracket and overall for the FAS.

For all participants of 24 (HFMSE) or 30 (RULM) months of age or more at baseline, changes from baseline in HFMSE and RULM will be summarized descriptively; in addition, mixed models with repeated measurement will be fitted that include the change from baseline as the dependent variable, and fixed effects of weight bracket, visit, and their interaction as well as covariate of baseline value. The least squares means and 95% 2-sided confidence intervals will be reported for each visit. Changes in total scores over time will be visualized by means of box-whisker plots and individual longitudinal trajectories. The number and proportion of participants with increases and with decreases in total scores compared to baseline (any, by more than 3, 6, 10 points inclusive) will be presented by visit and weight bracket.

The number and proportion of participants achieving each developmental motor milestone will be presented per visit by weight bracket and overall. In addition, summaries of achievements respective to baseline achievement status will also be generated separately.

2.6.3 Handling of intercurrent events

Changes in HFMSE and RULM and developmental motor milestone achievements will be summarized for all data available, only excluding data collected after the start of intake of prohibited medication with an impact on efficacy, if any, following a hypothetical strategy and assuming this intercurrent event occurring at random.

Following a composite strategy, in participants of the FAS dying before the achievement of a developmental motor milestone, the milestone is assumed not being achieved at any of the visits planned after the death occurred.

2.6.4 Handling of missing values not related to intercurrent event

Missing values not related to intercurrent events will not be imputed. All data of participants in the FAS will be presented as observed, collected and derived.

2.6.5 Sensitivity analyses

For HFMSE and RULM, in a sensitivity analysis of change in total score from baseline, on any missing data due to SMA-related death or invasive ventilation the HFMSE and RULM total scores will be set to 0, and on any missing data due to death for other causes to the last observed total score before death.

In further sensitivity analyses of changes from baseline in HFMSE and RULM total scores, missing item scores and “cannot test” assessments will be imputed by 0 scores for analysis. This applies as long as no more than 6 (HFMSE) and 3 (RULM) item scores per visit are missing or “cannot test”. If more items are missing or “cannot test”, total scores are not derived.

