4.6 Risks and benefits

Evidence from the completed and ongoing clinical studies continue to demonstrate the efficacy of OAV101. Substantial clinical efficacy of OAV101 across multiple endpoints-survival, motor function, developmental motor milestones, and ventilatory and nutritional endpoints has been established and confirmed in first-in-human and confirmatory studies. Long-term follow-up studies continue to support the durability of OAV101 efficacy, and participants continue to exhibit the achievement of additional milestones. Data spans pre-symptomatic and symptomatic participants.

Appropriate eligibility criteria and clinical safety monitoring criteria are included in this protocol. The risk to participants in this trial will be minimized by compliance with the eligibility criteria and study procedures, as well as close clinical monitoring and evaluation by an independent DMC.

The safety profile of OAV101 is described in the Investigator Brochure. The risks and benefits are derived from:

1. Non-clinical toxicology studies
2. Clinical studies for the treatment of symptomatic and pre-symptomatic participants with SMA who have 1, 2 or 3 copies of the *SMN2* gene and bi-allelic *SMN1* gene deletions at the proposed therapeutic dose of 1.1e14 vg/kg and the dose being proposed in this study
3. Long term follow-up study of participants who were administered OAV101 in clinical trials
4. US managed access program in participants with serious or life-threatening disease
5. Long-term registry of participants diagnosed with SMA
6. Post-marketing safety monitoring

The following are important identified and important potential risks associated with OAV101:

- Hepatotoxicity
- Thrombocytopenia
- Cardiac adverse events
- Dorsal root ganglia toxicity
- Thrombotic microangiopathy

Further details are outlined in the Investigator Brochure.

Risk of immunosuppression

All participants in the study will receive prophylaxis immunosuppression with prednisolone or equivalent corticosteroid to mitigate safety risks associated with inflammation ([Section 4.3](#)). The chronic use of corticosteroids may be associated with hypothalamic-pituitary-adrenal axis suppression, Cushing's syndrome and hyperglycemia which can be mitigated with adequate

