2.5 Analysis supporting primary objective(s)

2.5.1 Primary endpoint(s)

The primary endpoints include:

1. Incidence and severity of treatment emergent AEs and SAEs
2. Incidence of important identified and important potential risks
3. Change from baseline in vital signs, clinical laboratory, and procedure (eg ECG, echocardiogram) results

An AE is treatment-emergent, if it occurs or worsens after the start of the infusion of the investigational drug.

Important identified and important potential risks include the following AEs (see section 2.7.1.1 for detail):

- Hepatotoxicity
- Thrombocytopenia
- Cardiac adverse events
- Dorsal root ganglia toxicity

- Thrombotic microangiopathy

Vital sign parameters include height, weight, body mass index, blood pressure, respiratory rate, pulse, temperature, and oxygen saturation level. On Day 1, vital signs will be recorded pre-dose and then monitored post dose and at each visit.

Laboratory parameters in the scope of primary endpoints include platelets, troponin-I, and among chemistry variables alanine aminotransferase (ALT), aspartate aminotransferase (AST), glutamate dehydrogenase (GLDH), alkaline phosphatase (ALP), gamma glutamyl transferase (GGT), serum total bilirubin, direct bilirubin, and indirect bilirubin.

Cardiac procedures include ECG and echocardiogram. ECG parameters include QT, RR, and QTcF. Reviewed by local and central cardiologists, echocardiogram parameters include thrombus status, left ventricular ejection fraction (%), left ventricular fractional shortening (%), and left ventricular global longitudinal strain. ECG overall interpretation will be given.

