2.6.6 Supplementary analyses

No supplementary analysis is planned.

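### In the HFMSE/RULM sensitivity analysis, a death caused by OAV101 is scored more favourably than a disease death or invasive ventilation

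*SAP*

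**What the plan says.** SAP 2.6.5 has two branches for HFMSE and RULM data missing because of death. In the first, "on any missing data due to SMA-related death or invasive ventilation the HFMSE and RULM total scores will be set to 0". In the second, the totals are set "on any missing data due to death for other causes to the last observed total score before death". Neither branch mentions a death related to study treatment, and the SAP does not define an SMA-related death.

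No other rule brings death into the motor scores. The secondary estimand (SAP 1.2.2) gives a strategy for loss to follow-up for reasons other than death. The main analysis uses available data, and SAP 2.6.4 states: "Missing values not related to intercurrent events will not be imputed". SAP 2.6.6 adds: "No supplementary analysis is planned".

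The plan names the toxicities that it watches for. Protocol 4.6 introduces them with "The following are important identified and important potential risks associated with OAV101", and SAP 2.5.1 repeats them under "Important identified and important potential risks include the following AEs": hepatotoxicity, thrombocytopenia, cardiac events, dorsal root ganglia toxicity and thrombotic microangiopathy. On death in general, SAP 2.5.3 says: "It is anticipated that this intercurrent event is unlikely to occur during the study".

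**The concern.** On ordinary meaning, a death from hepatotoxicity, a cardiac event or thrombotic microangiopathy is not SMA-related, so it goes to the carry-forward branch. From then on the child is scored as holding the last motor total. A child who dies of the disease scores 0, and so does a living child whose assessment is missing because of invasive ventilation. The scoring therefore ranks a drug-caused death above both.

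That ordering is hard to defend in the one analysis in which death affects HFMSE and RULM. The study enrols heavier children than earlier OAV101 trials did, and safety is its primary objective, so a treatment-related death is a case the rule should handle sensibly. If the rule were settled only after such a death, the choice would be post hoc.

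**Working it through.** The plan gives no figure for this point. Its one computable figure, in SAP section 3, is a 90% chance of seeing at least one event with about 24 participants at 9% incidence. It reproduces as 1 − 0.91^24 = 0.896, and nothing below depends on it.

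**1. Which branch applies.** The cause of death decides:
- SMA-related: 0.
- OAV101 toxicity: not SMA-related on plain wording, so last observed score.
- Unrelated to either: last observed score.
- Mixed, for example respiratory failure during a toxicity event: undetermined, because SMA-related is undefined.

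**2. For how long.** The rule covers any data missing because of the death. Efficacy visits are at Weeks 4, 13, 26, 39 and 52 (SAP 2.1.1), so the value runs through Week 52.

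**3. What the child contributes.** Let b be the baseline total and g the change at the last assessment before death.
- Carry-forward: change = g. This is positive, zero or negative, and it is 0 if death precedes any post-baseline test.
- Score 0: change = −b.
- Difference: g − (−b) = b + g, which is the last observed total.

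Totals cannot fall below 0 (HFMSE runs 0 to 66 and RULM 0 to 37; Protocol 8.5.1.1 and 8.5.1.2). Carry-forward is therefore never less favourable than 0, and the two are equal only if the last total was 0.

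**4. Shift in the raw mean change at a visit.** Shift = (b + g)/n, with n the children in the summary.

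Assumed HFMSE values are b = 20 and last score 26, so g = 6 and b + g = 26:
- Overall, n = 24: 26/24 = 1.08
- Overall, n = 30: 26/30 = 0.87
- Bracket of 6: 26/6 = 4.33
- Bracket of 8: 26/8 = 3.25
- Bracket of 10: 26/10 = 2.60

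**5. Range over other assumed baselines (HFMSE, g = 3).**
- b = 10: (10 + 3)/10 = 1.3 in a bracket of 10; 13/30 = 0.43 overall.
- b = 40: (40 + 3)/6 = 7.17 in a bracket of 6; 43/24 = 1.79 overall.

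For RULM with b = 20 and g = 2, a bracket of 8 shifts by 22/8 = 2.75.

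**6. Denominator.** The values 24, 30 and 6 to 10 are enrolment targets. SAP 2.6.1 and 2.6.2 restrict change from baseline to children with a baseline score, aged at least 24 months (HFMSE) or 30 months (RULM) at baseline. The actual n may be smaller and the shift larger. The formula is for the raw mean; the repeated-measures LS means, which adjust for baseline, need not move by exactly this amount.

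**7. Chance that the rule is used.** The documents give no death rate. With an assumed per-child risk p of a death in the carry-forward branch, the chance of at least one in 24 is 1 − (1 − p)^24: 11% at p = 0.5%, 21% at 1%, 38% at 2% and 71% at 5%.

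**The case against.** The best defence is that the rule separates efficacy from safety. Disease-driven failure is scored 0, and toxicity is left to the safety analyses, which are primary here. SAP 2.7.1 tabulates treatment-emergent events leading to death, SAP 2.7.1.1.1 summarises serious and drug-related events of special interest, and SAP 2.7.2 lists and summarises deaths. Individual motor trajectories are plotted (SAP 2.6.2). With 24 to 30 children, a toxicity death would not go unnoticed. The main HFMSE/RULM analysis does not use the rule, no hypothesis is tested, and death is expected to be unlikely. All of this stands and limits the weight of the point. It does not explain why a drug-caused death should score above ventilation in a living child.

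Three stronger readings are tempting, and the documents do not support them:
- **That the rule credits such a child with a retained motor gain.** It keeps the last score, so a loss or no change is kept just as a gain is.
- **That the milestone rule treats the same death in the opposite direction.** SAP 2.6.3 covers only a child who dies before achieving a milestone; then "the milestone is assumed not being achieved at any of the visits planned after the death occurred". That also keeps the pre-death status, and the section does not turn a milestone already achieved into a failure.
- **That the sensitivity analysis cannot test the efficacy claim.** The SAP states no such purpose for it, and it is one sensitivity analysis of descriptive secondary endpoints.

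**Conclusion.** The point holds in a narrow form. Read literally, SAP 2.6.5 places a death from OAV101 toxicity in the carry-forward branch, so at every later visit it is scored more favourably than a disease death or invasive ventilation, unless the last total was already 0. With the assumed baseline of 20 and last score of 26, one such death shifts the mean change by about 1.1 points at n = 24 and 3.3 points in a bracket of 8. These sizes rest on assumed scores and enrolment denominators, not on plan figures.

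The effect is confined to one sensitivity analysis, is nil if no such death occurs, and hides nothing from the safety reporting. A reader might go further and infer that every death must score 0. The documents do not require this: it would count an accidental death as total motor loss, and carry-forward is a reasonable choice for a death unrelated to both disease and drug.

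**What to change.** Amend SAP 2.6.5 as follows:
- Set HFMSE and RULM totals to 0 for visits missing after a death that is SMA-related or judged related to OAV101 by the investigator or the sponsor. Leave the invasive-ventilation rule as it is.
- Carry the last total forward only for deaths judged unrelated to both SMA and OAV101.
- State that a death of mixed or undetermined cause goes to the 0 branch.
- Report the number of children in each category.

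The cost is small: an edit to one SAP paragraph, one programming condition and one line of counts. Relationship to treatment is already recorded for each adverse event (Protocol 10.1.1), and the Protocol summary already plans to report investigator and sponsor causality. No new data or visits are needed. The downside is that the sensitivity mean becomes less favourable if such a death occurs. The size of that penalty depends on the child's baseline, since a score of 0 gives a change of minus baseline; the existing 0 branch already has this property.
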